## B2bii. Biological measures

### *Physiological Measures*

1) Heart rate and blood pressure. After sitting for 5 minutes, the subject's radial pulse rate will be measured. After the heart rate measurements, blood pressure will be measured twice, 2 minutes apart for reliability. Measurements will be taken using a Critikon Dinamap (GE Medical Systems, Tampa, FL). Although acute increases in heart rate and blood pressure have been observed, most studies have shown a lack of sustained increases in heart rate and blood pressure from ST use [126]. On the other hand, a few studies have shown increased hypertension among ST users [127, 128] and one of the studies has implicated elevated blood pressure as the potential causal pathway for increased risk for fatal myocardial infarction observed [129].

2) Body weight. Subjects will remove their shoes, coats, sweaters, etc. and be weighed to the nearest 0.25 lb on an electronic scale.

### *Nicotine metabolism*

3) Nicotine metabolite ratio. This ratio is an indicator of CYP2A6 enzyme activity and is the ratio between two nicotine metabolites, cotinine and *trans*-3'-hydroxycotinine (3-HC). Because CYP2A6 is the primary enzyme associated with nicotine metabolism and also catalyzes the conversion of cotinine to 3-HC, the 3-HC:cotinine ratio is considered to reflect the enzymatic activity of CYP2A6 and reflect the extent of nicotine clearance rate (higher the ratio, the faster the clearance rate). This metabolite

ratio has been observed to be moderately correlated to CYP2A6 genotype and the rate of nicotine metabolism [20, 21, 130-133].

#### Biomarkers.

4) Biomarkers for tobacco exposure measures. Urinary total nicotine equivalents--total nicotine (free plus nicotine *N*-glucuronide) and its main metabolites, total cotinine (free plus cotinine *N*-glucuronide), total *trans*-3'-hydroxycotinine (3-HC) (free plus 3-HC *N*- and *O*-glucuronide)--which together account for 85-90% of the nicotine dose and is a useful measure of daily nicotine exposure, will be assessed by the [name] laboratory at the Masonic Cancer Center, University of Minnesota. Carbon monoxide, which is rapidly absorbed into the blood stream during smoke inhalation and binds with hemoglobin to form carboxyhemoglobin (COHb), will be measured using the Bedfont Micro Smokerlyzer® (Bedfont Scientific Limited, Kent, UK) device to verify abstinence from smoking. A spot urine samples will be collected at the orientation visit and at the clinic visit.

5) Biomarkers for carcinogen exposure and effect. The following urinary biomarkers of carcinogen exposure will be assessed: a) NNAL and NNAL-glucuronides (total NNAL), metabolites of the tobacco-specific carcinogen NNK; b) *N*'-nitrosonornicotine (NNN) and its glucuronides in urine (total NNN), reflecting the uptake of the tobacco-specific carcinogen NNN; c) the nitrosamino acids NPRO, a widely accepted biomarker of endogenous nitrosation, and MNPA, a biomarker of exposure to the carcinogen MNPA found in smokeless tobacco products; d) 1-HOP, a well established biomarker of exposure to PAH; e) phenanthrene tetraol, a marker for PAH. First urine void in the morning will be collected for the urine analyses [64]. The analyses will be carried out in the [name] laboratory using well established methods described in our previous publications [62, 134-136]. Results will be expressed per mg urinary creatinine.

For the sample collection at the other sites, staff will be trained on how to collect, process and send the urine samples. Urine samples will be collected, frozen and shipped on dry ice to Minnesota for analysis. The names and other identifying information will be stripped from the data before transmission and the file connecting the data with the subject number will be transferred via secure VPN in a separate file to Minnesota project staff. The file connecting the data to the identifying information of the participant will be stored at each site in a locked file cabinet and will be accessible only to approved study staff.

6) Cardiovascular Disease (CVD) Risk Factors. We will collect samples to measure CVD risk factors only at the Minnesota site to save costs. CVD risk factors will be analyzed at the University or Minnesota Medical Center Fairview, Collaborative Studies Clinical Laboratory, Minneapolis, MN. To date, most of the existing studies on CVD risk factors in ST users have been conducted in Sweden. A review of these studies shows that exclusive ST users do not demonstrate higher CVD risk factors (e.g., lipoproteins, biomarkers of oxidative stress and inflammation, endothelial function and platelet activation, carotid intima media thickness) compared to non-users among Swedish ST users and similar results have been observed with healthy young US snuff users [126, 138]. On the other hand, a few studies conducted with ST users in India have shown elevation in lipoproteins and triglycerides [139, 140]. Because of the limited knowledge of US products and a meta-analyses that shows an increased risk in CVD and stroke observed in the US population of smokeless tobacco users (although not the Swedish population [33] with the exception of fatal cardiovascular disease [128, 141]), the following CVD risk factors, which have been predominantly observed to be increased in cigarette smokers, will be assessed in our study: a) Lipoproteins, such as total plasma cholesterol, high and low density lipoproteins (HDL and LDL, respectively), and triglycerides. These markers were found to be dose-sensitive to cigarette exposure in our prior studies. Subjects will fast for 10 hours prior to blood draws. Preferably sampling will be done in early morning, but samples can be done mid-day according to work schedules of subjects as long as the subjects are fasting. b) C-reactive protein is considered to be an inflammatory marker or mediator and its release by the liver is stimulated by pro-inflammatory cytokines, including interleukin 6 (IL-6). Increases in C-reactive protein have been predictive of future vascular events and course of pre-existing vascular disease, and smoking has been found to modulate levels of this protein [e.g., 142, 143]. Several mechanisms by which C-reactive protein contributes to the risks of cardiac disease have been described [143, 144]. c) Fibrinogen is a marker for thrombosis

and is a glycoprotein involved in the coagulation response to vascular and tissue injury. Fibrinogen is also considered to contribute to vascular disease in other ways besides its role in thrombosis such as stimulating smooth muscle cell proliferation, promoting platelet aggregation and increasing blood viscosity [145]. Elevated fibrinogen levels have been found to be strongly predictive of cardiovascular morbidity and mortality [143]. Prior studies have shown a dose-response relationship between fibrinogen levels and number of cigarettes smoked [146]. d) White blood count, also an inflammatory marker, has been found to be higher in smokers than non-smokers [147, 148] and associated with cardiovascular disease [142] and in our studies was observed to be the most dose-related marker for cigarette reduction [84].

7) Buccal cells biomarkers. Although the grant proposal will not be able to bear the cost for analyses of buccal biomarkers, we will be collecting buccal cell samples to be placed in a biorepository with the hopes of obtaining future funding for their analysis. Buccal cells will be obtained through two methods (oral cheek swab and mouth wash for DNA extraction). These buccal cells will be frozen, stored and labeled in accordance to the procedures used in our NCI contract (N01-PC-64402) and will be made available to investigators associated with the contract or outside of this contract upon review of their proposal and approval from their respective IRBs. All samples will be de-identified. Examples of potential biomarkers include cellular autofluorescence (a method being tested by [name] at Roswell Park Cancer Institute), mitochondrial mutations in oral cavity cells (an analyses being tested by [name] at Georgetown University) and nf Kappa B p65 staining (an analyses conducted for NCI contract N01- CN-15000 by [name] at the University of Minnesota).

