### **B2. Procedures**

*Subject recruitment.* Subjects (N=600) will be recruited from a) Minneapolis/St. Paul, MN, b) Eugene, OR, and c) Morgantown, WV. Each site will recruit 200 subjects over the course of 2 years, with a total of 100 subjects recruited for each brand that is listed in Table 2. We anticipate no problems with recruitment. Surveys conducted in 2007 or 2006 estimated Minnesota and Oregon male ST prevalence of 6.0% and 6.5%, respectively. The 2006 West Virginia Adult Tobacco Survey estimated the male ST prevalence to be about 16%. Multiple avenues of recruitment will be pursued to ensure as representative of a sample as possible. These methods include radio, cable, newspapers (want ads and display ads), restroom stall ads, sporting good stores, WIC clinics, internet and press releases. The recruitment advertisements will state that daily ST users are needed for a study that examines the effects from ST use; blood (only at U of MN site), oral cells (only at U of MN site) and urine samples will be obtained. It will further state that subjects will be paid for participation. Potential adult subjects will be asked to call the research clinic number where the study will be explained, brief phone screening will be conducted, and interested and potentially eligible subjects will be asked to attend an orientation meeting. The brands of ST will not be listed on the advertisements to ensure that we are recruiting actual users of the brands rather than subjects who falsely claim using one of the brands of interest in order to obtain money for study participation. Subjects will be informed that the study determines the extent of exposure to toxicants and the effects of these exposures across different brands of ST.

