### **B2b. Measures and Schedule of Administration**

The following provides the measures that will be administered. Table 1 describes the measures to be obtained and the timing of the measurement. The majority of these measures have been used in our prior studies and have been found to be dose-sensitive to change in amount of smoking or ST use, or sensitive to switching products (e.g., conventional cigarettes to modified cigarettes, cigarettes to ST products).

Table 1. Schedule of visits and measures Study 1

	Visit	
	Orientation	1
Consent	X	
Baseline and Moderator Measures		
Demographics	X	
Medical History and Concomitant meds	X	X
Tobacco Use History and Exposure,	X (brief)	
Severson ST Dependency Scale	X	
Perceived Health Risk	X	X
Stages of Change		X
CES-D		X
PANAS		X
Perceived Stress Scale		X
Michigan Alcohol Screening Test,		X
NIAAA Alcohol Use Questionnaire		
Exposure and Lifestyle Measures		
Occupational Health History		X
ETS and Social Influences		X
Dietary – consumption of meats		X
IPAQ		X
Medical status (e.g., infections)		X

Novel Determinants and Measures of Smokeless Tobacco Use: Study 1

Daily Tobacco Use Diary	X (start at screen)	X
Vitals (Blood pressure and heart rate)		X
Weight		X
Concomitant Medications		X
Carcinogen Exposure Urinary total NNAL Total NNN Nitrosoamino acids NPRO and MNPA Phenanthrene tetraol 1-hydroxypyrene (1HOP)		X
Cardiovascular Measures (UMN only) Lipoproteins C-reactive protein Fibrinogen WBC		X X X X
 Buccal assay		X
 Nicotine and metabolites	X	X
 Product Constituent Testing		X
 Weight per dip	X	X
Carbon Monoxide		X

Buccal assays to be placed in biorepository for future analyses (UMN only)

Urinary total nicotine equivalents and nicotine metabolite ratio (3-HC:cotinine)

Product constituent testing will be conducted on a random sample of 30 tins for each brand of ST (10 brands from each site)

Estimated weight per dip will be calculated by averaging the weight of 3 typical daps

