### **C. Statistical analyses**

#### **C1. Analytic Approach**

##### ***Primary Aims***

1. To determine the toxicant exposure associated with currently marketed oral tobacco products with varying levels of toxicants and nicotine.

Subject characteristics will be examined across sites and ST users at each site will be compared to the characteristics of the respective state population of ST users. The outcomes for this study are the uptake of toxicants, as measured by biomarkers of exposure including NNAL, NNN, nitrosoamino acids,

1-HOP and total nicotine equivalents and biomarkers of effect such as CVD risk factors. The distribution of each biomarker will be examined to determine if a data transformation is necessary. From our previous experience, the distributions of many biomarkers are often skewed with a long right tail and need to be analyzed in the natural log scale. The two biomarker assessments for nicotine from each subject will be used to evaluate the reliability, as measured by the intraclass correlation. The two readings will then be averaged for the subsequent analysis. The geometric mean and the corresponding 95% confidence interval for the biomarkers will be calculated for each brand. The one-way analysis of variance (ANOVA) will be used to compare the mean toxicant levels between all six brands. If this global test is significant, then the Tukey's studentized range procedure will be used for pair-wise comparisons between brands, while maintaining an overall significance level of 5%.

2. To determine if toxicant and nicotine exposure is related to product factors such as the levels of these constituents (nicotine, NNK and NNN) in the products and patterns of use such as tins per week, dips per day, duration per dip, total dip duration (dip per day x duration per dip), weight per dip.

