## **C2. Power Considerations:**

The goal is to enroll 100 subjects for each of the six brands listed in Table 2. The mean toxicant uptake level is expected to vary between brands; however, the standard deviation (SD) should

be similar for all brands. This is the common SD and is equivalent to the root of the Mean Square Error (MSE) from the one-way ANOVA. With a total of 600 subjects, this F-test will have 92% power to detect a significant difference at the 0.05 level if the brands with the largest and smallest means differ by at least one-half the common SD. Therefore, if the common SD for the biomarker was 10 units, then there would be a 92% chance that we find a significant difference between brands if the biggest and smallest means were at least 5 units apart. This analysis was done using Power Analysis and Sample Size (PASS) 2005 by NCSS, Inc.

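### The stated 92% power assumes 600 subjects, but the cardiovascular outcomes of Primary Aim 1 are measured only in Minnesota's 200, where like-for-like power is about 41%

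*Combined protocol and SAP*

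**What the plan says.** Section C1 lists the outcomes under Primary Aim 1. After the urinary exposure markers it adds "biomarkers of effect such as CVD risk factors". The analysis it then gives is: "The one-way analysis of variance (ANOVA) will be used to compare the mean toxicant levels between all six brands". Tukey comparisons follow if the global test is significant. No other brand comparison is described for the CVD markers.

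Item 6 of B2bii restricts them to one site: "We will collect samples to measure CVD risk factors only at the Minnesota site to save costs". Table 1 in B2b likewise marks lipoproteins, C-reactive protein, fibrinogen and white cell count as University of Minnesota only. Section B2 fixes the size of that site: "Each site will recruit 200 subjects over the course of 2 years".

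Section C2 sets the overall target, "The goal is to enroll 100 subjects for each of the six brands listed in Table 2", and gives one power statement: "With a total of 600 subjects, this F-test will have 92% power". It is for a 0.05 test and a gap of at least half the common SD between the highest and lowest brand means. C2 illustrates it with an unspecified biomarker and gives no power or detectable difference for 200 subjects.

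**The concern.** The power calculation uses three times as many subjects as will supply CVD data. Someone who uses C2 to judge what the six-brand comparison can detect finds a single figure and nothing to say that one named class of outcomes falls outside it. What is at stake is how a non-significant CVD comparison is read. At 92% power, a miss of a true half-SD range would be rare. At about 41%, it would be missed about 59% of the time (100 − 41).

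**Working it through.** **Inputs.** Six brands, one-way ANOVA (C1). 600 subjects, 100 per brand, two-group gap expressed in units of a common SD, range of means 0.5 SD, alpha 0.05 (C2). 200 subjects per site (B2). CVD sampling at Minnesota only (B2bii item 6, Table 1). *Assumption:* the 200 Minnesota subjects divide equally over the brands, 200/6 = 33.3 each. The documents fix 100 per brand only across sites.

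**Formula.** Power = P(F′ > F₀.₉₅), where F′ is noncentral F with 5 and N − 6 degrees of freedom and noncentrality λ = n × Σ(μᵢ − μ̄)². Here n is the number per brand and the means are in SD units.

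**Sum of squares by pattern, range 0.5 SD.**
- Four brands at the midpoint: 2 × 0.25² = 0.125.
- Equally spaced: 2 × (0.25² + 0.15² + 0.05²) = 0.175.
- One brand differs: 0.5² × 5/6 = 0.208.
- Three low, three high: 6 × 0.25² = 0.375.

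**Step 1: reproduce the plan's figure, then change only N.**

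| Pattern | λ, n = 100 | Power, N = 600 | λ, n = 33.3 | Power, N = 200 |
|---|---|---|---|---|
| Four at midpoint (least favourable) | 12.5 | 78.4% | 4.17 | 29.5% |
| Equally spaced | 17.5 | 91.6% | 5.83 | 41.0% |
| One brand differs | 20.8 | 95.9% | 6.94 | 48.4% |
| Three low, three high | 37.5 | 99.9% | 12.5 | 77.5% |

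C2 does not state its pattern. Of these four, only equal spacing reproduces 92%, so 41% is the like-for-like figure at N = 200.

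**Step 2: is there a ceiling?** For a fixed range R, Σnᵢ(μᵢ − μ̄)² cannot exceed N × (R/2)² however the subjects are split. Here that is 200 × 0.25² = 12.5, the value for three low and three high. So about 77% is the most that six groups and 200 subjects can give at a range of 0.5 SD.

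**Step 3: range needed at N = 200.**
- 92% power: 0.88 SD equally spaced, 1.04 SD least favourable.
- 80% power: 0.75 SD and 0.89 SD.

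Check: the sum of squares is 0.7R² for equal spacing (0.175/0.25) and 0.5R² for the least favourable pattern (0.125/0.25). Then 33.3 × 0.7 × 0.88² ≈ 18.1 and 33.3 × 0.5 × 1.04² ≈ 18.0, the same noncentrality to rounding.

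**Step 4: small changes in N.** With exactly 33 per brand (N = 198), the figures are 40.6% and 29.2%. With 180 analysable subjects they are 36.9% and 26.6%.

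**The case against.** The strongest reply is that C2 never claims 92% for the CVD markers. It introduces the calculation in terms of toxicant uptake, makes the figure conditional on 600 subjects, and the ANOVA sentence in C1 refers to toxicant levels. Lipids and inflammatory markers are not toxicants, and the single-site restriction is disclosed with its reason. This has force: the fault is a gap in scope. It does not remove the point. C1 names the CVD markers as outcomes under this aim and offers no other analysis, so on the narrower reading they have no power statement at all, and the same sentence is needed.

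The second reply is that the CVD power depends on things the documents leave open: the pattern of brand means and the brand mix at Minnesota. That stands. A reader might take 30% to 41% as the whole range at 0.5 SD, but it is not. It runs from the least favourable pattern to the one C2 implies, and clustered brands give 48% to 77%. An uneven split could lower the figures further if the extreme brands are scarce at Minnesota.

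Three stronger inferences are tempting and not supported. The first is that the 92% is miscalculated; it reproduces at 600 subjects. The second is that a null CVD result will be presented as showing no difference between brands; the plan says nothing of the kind, and C1 already provides geometric means with 95% confidence intervals by brand. The third is that the CVD comparisons must be reclassified as exploratory; that is one option, and the documents do not require it.

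**Conclusion.** The point holds as a mismatch between the power statement and the sample for one class of Primary Aim 1 outcomes. On C2's implied assumptions, power for the CVD comparisons is about 41%, against a stated 92%. The minimum under an equal split is about 30%, and no pattern brings it above about 77%. The figures rest on six groups as C1 and C2 state, a range of exactly 0.5 SD, a common SD and, except for the ceiling, an equal brand split at Minnesota. They make no allowance for missing samples or for testing several markers. The 92% remains valid, for equally spaced means, for outcomes measured at all three sites.

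**What to change.** In C2:
- Limit the 92% statement to outcomes measured at all three sites, and name the pattern of means it assumes (equally spaced reproduces it).
- Add a sentence for the CVD markers along these lines: measured at Minnesota only, 200 subjects, equal brand split assumed; power is about 41% for a range of 0.5 SD with equally spaced means (about 30% in the least favourable pattern); 92% power needs a range of about 0.88 SD (1.04 SD in the least favourable pattern).
- State that non-significant CVD brand comparisons will be interpreted against those figures, using the brand means and 95% intervals already planned in C1.

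The cost is wording, together with a less favourable stated power for the CVD outcomes. No subjects, assays or sites are added, and the decision to sample at one site is unaffected.

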### ***B2c. Product constituent testing***

In collaboration with the Center for Disease Control and Prevention, we will analyze the constituents of the smokeless tobacco products (un-ionized nicotine, tobacco specific nitrosamines and pyrene) used by our participants. This information will be related to the biomarker data. A random sample of tins of unused ST from 10 subjects for each brand of ST at each site will be analyzed. For Study 1, 180 subject samples (10 random subjects x 6 brands x 3 sites) will be analyzed. The tins will be labeled with the subject number, site identification, date of collection, brand of ST and tin lot number. Samples will be stored in the freezer until a batch is shipped to CDC on dry ice. Subjects will be reimbursed for their tin of ST. The major advantage of taking tins from the subjects is that they may more accurately reflect actual levels of toxicants. Prior studies have shown change in TSNAs based on storage conditions. CDC will analyze samples for NNAL, NNN, NAT, NAB, PAHs, Nitrosamino acids (MNPA & NIS will be added to CDC usual analyses).

### ***B2d. Tobacco Products***

For Study 1, usual brand of ST products will be used. We chose products that had substantial market share and showed a range in nicotine level and in NNK and NNN levels [4, 46, 75, 151]. Table 2 shows the brands that were chosen for testing. Free/unprotonated nicotine levels were considered high (H) if they were > 5 mg/g, medium (M) if they were between 2-5 mg/g and low if they were < 2 mg/g [3]. TSNA levels were based on a classification that was developed by [name] ([name], report for WHO, TobReg). High (H) levels were NNN plus NNK > than 10 µg/g, Medium (M) levels were NNN plus NNK from 2-10 µg/g, and Low (L) levels were NNN plus NNK < 2 µg/g. Products that are in the Low range for both nicotine and TSNAs tend not be manufactured.

Table 2

Group	Product	Test Date	# Tins/ Regions	Nicotine (mg/g wet)	NNK+NNN (µg/g wet)	Nicotine Group	TSNA Group
1	Camel Snus (All Flavors)	Fall 2010		2.65		Low	Low
	Marlboro Snus (All Flavors)						
	Skoal Long Cut Mint	Fall 2011	3 / 2	1.2	1.23		
	Skoal Fine Cut Original	Spring 2011	1 / 1	2.79	1.88		
2	Copenhagen Long Cut Original	Fall 2010	1 / 1	3.51	2.55	Med	Med
	Kodiak Wintergreen	Spring 2010	9 / 3	4.51	2.73		
	Skoal Bandits Wintergreen	Spring 2010	11 / 3	3.05	3.72		
	Skoal Pouches Straight	Spring 2011	1 / 1	4.02	2.58		
	Skoal Pouches Wintergreen	Spring 2011	1 / 1	3.89	2.81		
	Grizzly Long Cut Straight	Spring 2010	5 / 2	4.23	3.84		
	Skoal Long Cut Straight	Spring 2010	9 / 3	3.15	3.11		
3	Grizzly Long Cut Mint	2010 summary		7.58	3.72	High	Med
	Grizzly Long Cut Wintergreen	Spring 2010	4 / 2	5.12	3.05		
	Grizzly Pouches Wintergreen	Spring 2011	1 / 1	6.25	3.71		
	Skoal Pouches Mint	Spring 2011	1 / 1	5.19	2.15		
	Kodiak Pouches Wintergreen	Spring 2011	1 / 1	5.88	3.44		
4	Grizzly Fine Cut Regular	Spring 2011	1 / 1	4.41	15.3	Med	High
6	Kodiak Long Cut Mint	Spring 2011	1 / 1	3.9	1.91	Med	Low
	Kodiak Long Cut Straight	Spring 2011	1 / 1	4.06	1.88		
8	Copenhagen Fine Cut Original	Spring 2010	9 / 3	2.43	3.45	Low	Med
	Copenhagen Long Cut Straight	2010 summary		2.56	2.07		
	Grizzly Pouches Straight	Spring 2011	1 / 1	0.48	4.0		
	Skoal Long Cut Classic	Spring 2011	1 / 1	2.88	2.88		
	Skoal Long Cut Wintergreen	Spring 2011	1 / 1	2.7	2.51		

Nicotine Group	mg/g wet weight
Low	<3
Medium	3-5
High	>5

